### **5.3 Subject Withdrawal**

1. Subjects or HCPOA can terminate study participation and/or withdraw consent at any time without prejudice.
2. Subjects who withdraw from the study who have received study treatment will not be replaced. Subjects who have never received study treatment can be replaced.
3. The investigator may withdraw subjects if they are lost to follow up, non-compliant with study procedures or if the investigator determines that continued participation in the study would be harmful to the subject or the integrity of the study data.
4. Discontinuation of the study: the study sponsor, FDA and IRB all have the right to terminate this study at any time.

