**Study Drug:**

- SARS-CoV-2 convalescent plasma 2 units
- Study drug will be administered as a single intravenous infusion

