### **4.2 Study Definitions:**

1. Enrolled: From time consented to participate until designated as a screen failure or have either been discontinued from the study or completed it.
2. Screen Failures: signed informed consent, but then determined to be ineligible or withdraws before being treated.
3. Discontinued: enrolled, but then withdrawn by investigator or subject withdraws consent
4. Completed: Subjects are considered to have completed when they are followed through day 60 or day of death if death occurred prior to day 60

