### **11.2.1 SAEs are reported in the following manner:**

All fatal or life-threatening or unexpected and suspected SAEs will be reported to the IRB and all applicable agencies within 24 hours and all other SAEs (non-fatal or non-life-threatening) within 4 calendar days of study site staff awareness.

- Every SAE regardless of suspected causality (e.g., relationship to study drugs or study procedure) occurring after the subject has signed the consent through the 30 days after the last dose of study drugs, AND only SAEs occurring more than 30 days after the last dose of study drugs that the investigator suspects a causal relationship to study plasma, must be reported in the study database SAE section. These will also be reported to the ISM ([name] as below) and the IRB. All transfusion related AEs and SAEs have to be reported to the hospital blood bank additionally in order to start a transfusion AE investigation.
- All grade 4 and 5 SAEs and any other expedited SAE report to IRB must also be reported to FDA (MedWatch 3500A described below) within five calendar days of MCW study staff's awareness.

- In addition: if the SAE is unexpected and has a suspected relationship to the study drug, site must create a reportable event notice with the MCW IRB, ISM and complete a MedWatch 3500A and submit to FDA:
  - US FDA MedWatch 3500A found here:  
<http://www.fda.gov/Safety/MedWatch/HowToReport/DownloadForms/default.htm>

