### **11.2.3 Adverse Events Not Meeting SAE Definition**

- Any medical condition that is present at the time that the participant is screened will be considered as baseline condition and captured on the baseline CRF form, not reported as an AE. All new or worsening AEs that occur after starting study drug until 30 days post last dose of study plasma will be tracked and followed until resolution, stabilization of the event as chronic, subject withdraws consent, or is lost to follow-up (including subjects who discontinue early).
- Changes in the grade of an AE will be documented in the AE CRF to allow an assessment of the duration of the event at each level of severity to be performed. Information to be collected includes event description, time of onset, clinician’s assessment of severity, expectedness, relationship to study product (assessed only by those with the training and authority to make a diagnosis), and time of resolution/stabilization of the event.

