### **11.3 Reporting Interval**

All AEs and SAEs will be documented from consenting until study completion at 60 days from study infusion or death or discontinuation from the study. All AEs and SAEs will be followed until resolution even if this extends beyond the study-reporting period. Resolution of an adverse event is defined as the

return to pre-treatment status or stabilization of the condition with the expectation that it will remain chronic.

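### Sections 4.2, 5.3 and 11.3 together let an investigator's withdrawal decision after the single infusion end documentation of new adverse events, which contradicts section 11.2.1

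*Combined protocol and SAP*

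**What the plan says.** The Protocol Summary gives plasma once: "Study drug will be administered as a single intravenous infusion". Section 5.3 then sets out when a subject may be taken off study. It begins "The investigator may withdraw subjects if they are lost to follow up, non-compliant with study procedures" and adds a further ground, "if the investigator determines that continued participation in the study would be harmful to the subject or the integrity of the study data". None of these grounds is confined to the period before infusion. The same section plainly expects withdrawals after treatment: "Subjects who withdraw from the study who have received study treatment will not be replaced".

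Section 4.2 fixes the status of such a patient: "Discontinued: enrolled, but then withdrawn by investigator or subject withdraws consent". Section 11.3 documents all AEs and SAEs from consent "until study completion at 60 days from study infusion or death or discontinuation from the study". Its next sentence follows AEs and SAEs to resolution, even past the reporting period.

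Two other sections set different windows. Section 11.2.1 requires "Every SAE regardless of suspected causality" from consent to 30 days after the last dose, and after that only SAEs the investigator suspects are due to plasma. It has no exception for withdrawal. Section 11.2.3 tracks new or worsening AEs to 30 days after plasma, until resolution, stabilization, withdrawal of consent, or the point where the subject "is lost to follow-up (including subjects who discontinue early". Withdrawal by the investigator is not in that list by name.

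**The concern.** Once the only infusion has been given, taking a patient off study cannot reduce exposure to plasma. It can spare the patient research procedures, but under 11.3 it also ends documentation of new events. The person making that decision works in an open-label, single-arm trial and already knows how the patient is doing. If withdrawal for harm or non-compliance goes with a worse course, the lost follow-up depends on outcome, and there is no control arm with a similar loss to compare against.

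Three results are exposed: the cumulative incidence of plasma-attributed SAEs, which section 4.1 defines over the whole study period; the proportions with an SAE and with a Grade 3 or higher event (section 7.1); and 60-day mortality (section 7.5.2). Section 7.1 has no rule for patients withdrawn early. Staff who follow 11.3 and staff who follow 11.2.1 would also handle the same withdrawn patient differently, each with a section of the protocol on their side.

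**Working it through.** **Step 1: the sections side by side.** Take an infused patient whom the investigator withdraws, and who has not withdrawn consent.

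| Event | 11.3 | 11.2.1 | 11.2.3 |
|---|---|---|---|
| Recorded before withdrawal | Kept, followed to resolution | Reported if serious | Tracked; see step 2 |
| New SAE, to day 30 | Not documented | Required, any cause | Tracks AEs; see step 2 |
| New non-serious AE, to day 30 | Not documented | Not covered | See step 2 |
| New SAE, days 31–60, plasma suspected | Not documented | Required | Outside window |
| New SAE or death, days 31–60, plasma not suspected | Not documented | Not required | Outside window |

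Rows 2 and 4 are direct contradictions between 11.3 and 11.2.1. Row 5 is a gap: for this patient none of the three sections asks for the event.

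**Step 2: section 11.2.3.** The parenthesis about early discontinuers can be read two ways. If it describes who is tracked, 11.2.3 contradicts 11.3. If it describes who counts as lost to follow-up, tracking ends for them and the sections agree. The first reading is the more natural, but the finding does not rest on it; 11.2.1 is enough.

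**Step 3: windows for patients who stay on study.** Section 11.3 runs to day 60 for all AEs and SAEs. Section 11.2.3 stops at day 30, and 11.2.1 narrows to suspected SAEs at day 30. The mismatch therefore exists even without a withdrawal.

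**Step 4: what is not affected.** The respiratory deterioration endpoint in section 4.1 closes 12 hours after infusion, so it is largely complete before any withdrawal matters. The section 7.6 designs reproduce and do not depend on this point: Cohort 1 (41 subjects, success at 14 or more) has exact one-sided alpha 0.0242 and power 0.822; Cohort 2 (90 subjects, success at 44 or fewer) has alpha 0.0213 and power 0.802.

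**Step 5: scale.** The plan gives no figure for withdrawals or SAEs. If k patients have their only SAE after withdrawal and it goes unrecorded, the proportion falls by k/n:

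- Cohort 1, n = 41: k = 1, 3, 5 gives 2.4, 7.3, 12.2 points.
- Cohort 2, n = 90: k = 1, 3, 5 gives 1.1, 3.3, 5.6 points.

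A patient with an SAE already recorded still counts, so a second, missed SAE changes nothing in that proportion.

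As an assumed illustration, pooled over 131 although the plan analyzes the cohorts separately: with 10 patients truly having an attributed SAE, 10/131 = 7.6% (Clopper-Pearson 95% interval 3.7–13.6%). Missing 1, 3 or 5 gives 9/131 = 6.9%, 7/131 = 5.3% or 5/131 = 3.8% (the last with interval 1.3–8.7%). These are scenarios, not estimates.

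**The case against.** The strongest reply is that the protocol already keeps safety collection going. Section 11.2.1 demands every SAE to day 30 with no withdrawal exception, and 11.3 itself follows recorded events to resolution. Table 1 also shows adverse event monitoring throughout the study period. This reply stands against the inference a reader might draw that safety collection simply stops at withdrawal, or that the patients most likely to show harm drop out of the data. A patient whose breathing worsens after plasma and who is withdrawn on day 2 has that event on record, and its outcome, including a fatal one, is followed. Nothing in the plan removes infused patients from a denominator.

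A reader might also infer that one lost event could suppress the study halt, since section 12.2 acts on a single product-associated SAE. The documents do not show this. An event that prompts withdrawal has already been seen, is reportable under 11.2.1, and is reviewed in real time by the independent safety monitor. Only a new, later, product-associated SAE could be missed, and only if staff followed 11.3 over 11.2.1.

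Nor is a lower 60-day mortality established. Section 7.5.2 names one censoring situation, a routine discharge without later contact, and does not mention investigator withdrawal. Section 11.3 governs AE and SAE documentation, not survival follow-up. The bias arises only if withdrawn patients are censored and their prognosis is worse. Likewise, nothing says a withdrawn Cohort 2 patient would be scored as free of the primary endpoint.

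Finally, withdrawal after infusion has a legitimate use: it can spare a deteriorating patient research draws of about 30 ml each. That is a reason to keep the power and limit its effect.

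None of this answers the conflict between 11.3 and 11.2.1, or the days 31–60 gap.

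**Conclusion.** The plan contradicts itself on whether new adverse events are documented after the investigator withdraws an infused patient. Section 11.3, read with 4.2 and 5.3, ends documentation. Section 11.2.1 requires SAEs to day 30 regardless, and 11.2.3 probably conflicts with 11.3 as well. After day 30, an SAE or death not suspected to be plasma-related is required by none of the three, although mortality is assessed to day 60.

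The consequence is a possible downward bias in the SAE and Grade 3 or higher proportions, and in 60-day mortality if such patients are censored. It rests on two assumptions that the documents neither confirm nor exclude: that such withdrawals occur, and that they are related to outcome. Its size cannot be computed; per patient affected it is 2.4 points in Cohort 1 or 1.1 in Cohort 2. The change is worth making because the conflict is plain and the remedy is cheap.

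**What to change.** Reconcile the sections on data collection:

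- **Section 11.3:** replace discontinuation from the study, as an end of documentation, with withdrawal of consent to follow-up.
- **Section 5.3:** state that after infusion, withdrawal by the investigator stops research procedures only. AE, SAE and vital-status collection, by chart review or phone, continues to day 60 for every infused patient unless consent to it is withdrawn.
- **Sections 11.2.1 and 11.2.3:** align the 30-day windows with the 60-day window in 11.3, and reword the parenthesis in 11.2.3 so that it has one meaning.

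Removing data integrity as a ground for withdrawal is optional; once 5.3 limits what withdrawal does, that ground no longer threatens follow-up.

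The cost is a wording amendment and slight extra follow-up work. Section 8 already accepts phone contact at day 28, and section 15.1 already allows data to be abstracted from medical records. The cohort sizes and the primary tests do not change.

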### **6. Treatment**

1. Study drug: The investigational product is anti-SARS-CoV-2 convalescent plasma obtained from patients identified as having recovered from COVID-19 as per Versiti plasma collection protocols.
2. Donors and samples will have been screened for transfusion-transmitted infections (as per current AABB and FDA standards) both through the use of the uniform donor questionnaire and FDA mandated blood donor screening tests by Versiti.
3. ABO compatible plasma will be used to reduce risk of hemolysis.

#### **6.1 Rationale for doses**

Recommended dose will be 2 units of plasma for all patients.

#### **6.2 Study drug administration**

- Drug will be administered once consent, eligibility confirmation, enrollment, and screening/baseline procedures have been completed.
- Infusion rate  $\leq$  500 mL/hour.
- Pretreatment to minimize transfusion reactions (e.g. acetaminophen, diphenhydramine) may be given per investigator and clinical care team discretion.
- If an AE develops during infusion, the infusion may be slowed or stopped as per investigator's decision.
  - Most reactions to plasma are relatively minor and the infusion can generally be continued. Infusion site burning and non-allergic systemic effects can generally be managed with slowing of the infusion. Infusion can generally be continued in cases of itching or hives after pausing the transfusion, administering antihistamines, and observing the patient for worsening symptoms.
  - Severe allergic reactions such as, bronchospasm and hypotension, and may require discontinuation of the infusion.

## 6.3 Concomitant medications

Concomitant medications will be documented on the CRF and these include:

- Prescription medications
- Any other clinical trials
- Over the counter medications
- Herbal treatments/nutritional supplements
- Blood products administered

## 7. Statistical considerations

Patients will be enrolled in 2 cohorts independent of each other. Cohort 1 will consist of 41 patients who are admitted to the ICU. Cohort 2 will consist of 90 patients who are admitted to a non-ICU floor. The two cohorts will be analyzed independently. For sample size considerations please see section 7.6.

For each cohort, descriptive summaries of continuous and other numeric variables will consist of the summary statistics: median, minimum and maximum values. Categorical variables will be summarized by the frequency and proportion of subjects falling into each category. Unless otherwise indicated, percentages in tables will be column percentages, using the total number of observations in the population as the denominator. Exact confidence intervals for binomial proportions will be derived using the Clopper-Pearson method.

### 7.1 Analysis of AE data

Analysis of AE data will primarily be descriptive based on MedDRA coding of events. The proportion of subjects experiencing an SAE and the proportion experiencing a Grade 3 or higher event will be presented.

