## **PROTOCOL SUMMARY:**

An Open label, Phase 2 Study Evaluating the Efficacy and Safety of High-Titer Anti-SARS-CoV-2 plasma in hospitalized patients with COVID-19 infection

**Clinical Phase:** 2

**IND Sponsor:** Medical College of Wisconsin; [name] [name]

**Conducted by:** Medical College of Wisconsin in collaboration with Versiti as plasma source.

**Sample Size:** 131 patients in 2 cohorts (ICU cohort called cohort 1 and a hospitalized non-ICU cohort or cohort 2)

**Study Population:** Hospitalized COVID-19 patients  $\geq 18$  years of age with severe symptoms as defined in inclusion criteria and within 21 days of symptom onset.

**Study Duration:** April 15, 2020 to December 31, 2020

**Study Design:** This is an open label phase 2 trial assessing the efficacy and safety of anti-SARS-CoV-2 convalescent plasma in hospitalized patients with acute severe respiratory symptoms from COVID-19. Symptomatic patients with clinical or radiological interstitial COVID-19 pneumonia and within 21 days of onset of symptoms will be enrolled in 2 cohorts – an ICU cohort and a hospitalized non-ICU cohort.

**Study Assessments:** Refer to Table 1 and Section 8

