### **Primary Safety Objective:**

Evaluate the safety of treatment with high-titer anti-SARS-CoV-2 plasma in hospitalized patients with COVID-19 respiratory symptoms.

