### **Primary Safety Endpoints:**

1. Rapid deterioration of respiratory or clinical status on transfusion of SARS-CoV-2 convalescent plasma due to presumed antibody dependent enhancement or other mechanisms. Since patients in this study are already in respiratory distress, further worsening of respiratory status will be defined as below and causes attributed by treating physician. Any escalation of oxygenation or ventilatory needs within the 12 hours after plasma infusion will be considered as a deterioration. This includes new requirement for supplemental oxygen in a person not on oxygen, an increase of >25% in FiO2; need for non invasive or invasive mechanical ventilation in subjects not requiring these at the time of infusion. In patients already on mechanical ventilation, an increase in PEEP and or FiO2 of >25% will also be considered a respiratory deterioration.
2. Cumulative incidence of all serious adverse events attributed to plasma therapy during the study period: transfusion reaction (fever, rash), transfusion related acute lung injury (TRALI), transfusion associated circulatory overload (TACO), transfusion related infection

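### Section 7.1 states no analysis for either primary safety endpoint, and no pooled estimate of plasma-attributed SAEs is planned

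*Combined protocol and SAP*

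**What the plan says.** Section 4.1 sets one safety objective for the whole trial: "Evaluate the safety of treatment with high-titer anti-SARS-CoV-2 plasma in hospitalized patients with COVID-19 respiratory symptoms". Two primary safety endpoints follow. The first is rapid deterioration on transfusion, with the operative rule "Any escalation of oxygenation or ventilatory needs within the 12 hours after plasma infusion will be considered as a deterioration" and separate thresholds for patients already ventilated. The second is "Cumulative incidence of all serious adverse events attributed to plasma therapy during the study period".

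Section 7.1 is the only safety analysis in the statistical section. It has two sentences. The first is general: "Analysis of AE data will primarily be descriptive based on MedDRA coding of events". The second names the summaries: "The proportion of subjects experiencing an SAE and the proportion experiencing a Grade 3 or higher event will be presented". Neither mentions attribution to plasma, the 12-hour window or cumulative incidence.

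Section 7.3 lists only the two efficacy endpoints as primary, and Section 7.4 serves those. Section 7.5 gives most of the secondary endpoints their own subsections; the primary safety endpoints have none. On pooling, Section 7 says "The two cohorts will be analyzed independently", and Section 5 says the same. No analysis of all 131 patients is described.

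**The concern.** The quantity that Section 7.1 will present differs from the quantity the protocol calls its primary safety endpoint. Under Section 11.2, death, life-threatening events and a longer hospital stay all make an event serious. Section 11.2.1 captures every SAE for 30 days whatever its suspected cause. In hospitalised COVID-19 patients the disease itself will produce such events. With no control arm, a proportion that mixes them with transfusion reactions cannot show which is which. The attributed-SAE endpoint exists to attempt that separation.

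The 12-hour endpoint can also be missed. Newly needing oxygen, or a rise of more than 25% in FiO2, counts as deterioration under Section 4.1 but need not be an SAE or a Grade 3 event.

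Two things are at stake. If the summary is not fixed in advance, the choice of safety measure is left until the data have been seen. And the trial would give up precision on rare reactions that its own sample can supply.

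**Working it through.** **The plan's own figures.** The summary gives "131 patients in 2 cohorts". Section 7 gives 41 for Cohort 1 and 90 for Cohort 2, and 41 + 90 = 131. The cohort sizes come from efficacy power only (Section 7.6). Exact binomial checks agree with them: success at 14 or more of 41 (20% against 40%) has one-sided alpha 0.0242 and power 82.2%; success at 44 or fewer of 90 (60% against 45%) has alpha 0.0213 and power 80.2%. Both meet the plan's target of at least 80%. The documents state no safety rate or safety precision to reproduce.

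**Endpoint against analysis.**

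| Primary safety endpoint (4.1) | Named in 7.1? | Nearest item in 7.1 | What differs |
|---|---|---|---|
| Deterioration within 12 hours | No | Grade 3+ proportion | No time window; milder escalations can be missed |
| Plasma-attributed SAEs | No | SAE proportion | No attribution filter |

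**Precision for attributed SAEs.** Section 7 names Clopper-Pearson for binomial proportions. I assume the two-sided 95% level that Section 7.4 uses for efficacy. With zero events the upper limit is U = 1 − 0.025^(1/n):

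- n = 41: 1 − 0.025^(1/41) = 0.0860, or 8.6%
- n = 90: 1 − 0.025^(1/90) = 0.0402, or 4.0%
- n = 131: 1 − 0.025^(1/131) = 0.0278, or 2.8%

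With one event, the upper limit is the 97.5th percentile of Beta(2, n − 1): 12.9%, 6.0% and 4.2% in the same order.

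**Chance of seeing at least one event**, 1 − (1 − r)^n. The documents give no reaction rate, so r from 1% to 5% is an assumed range:

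| Assumed r | n = 41 | n = 90 | n = 131 |
|---|---|---|---|
| 1% | 33.8% | 59.5% | 73.2% |
| 2% | 56.3% | 83.8% | 92.9% |
| 5% | 87.8% | 99.0% | 99.9% |

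**How wide the unfiltered SAE proportion would be.** The documents give no SAE rate either, so this too is an assumed range. For n = 90 the exact 95% intervals are 12.3% to 29.8% at 18/90 (20%), 29.8% to 50.9% at 36/90 (40%) and 49.1% to 70.2% at 54/90 (60%). The half-widths are about 9 to 11 percentage points. Whatever the true rate, the more basic limit is that one unfiltered proportion in a single arm carries no information on cause.

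**Follow-up window.** Section 11.3 documents all AEs and SAEs to day 60. Section 11.2.3 tracks new or worsening AEs to 30 days after plasma, although its heading concerns non-serious events. Section 11.2.1 requires every SAE to 30 days and, after that, only SAEs with a suspected link to plasma. The endpoint refers only to the study period. The analysis section gives no window.

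**The case against.** The strongest reply is that nothing is lost, because the rest of the plan fills the gap. Section 7 gives a default for categorical variables (frequency and proportion) and an exact interval for binomial proportions. A MedDRA-coded description would show TRALI, TACO and transfusion reactions as separate terms. Sections 11.2.3 and 11.3 have relationship to product recorded and assessed. The independent safety monitor reviews each SAE as it occurs, and under Section 12.2 one product-associated SAE stops enrollment and dosing for review.

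Much of this stands. A reader might infer that the primary safety question goes unanswered. The documents do not support that: the data and a general method are there. What is missing is the link. No text applies the defaults to these endpoints or states the infused-patient denominator. The halting rule governs conduct and yields no reported estimate.

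A reader might also take the 45% and 60% in Section 7.3 as the expected SAE rate and conclude that a reaction rate of a few percent would be hidden by a known amount. Those figures are the clinically meaningful and null values of the Cohort 2 efficacy composite, which counts ICU transfer and intubation. They are not SAE rates, so any masking figure is an assumption.

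Finally, a reader might call the lack of pooling an error. Separate cohort analysis is a deliberate choice, stated twice. For 12-hour deterioration it is also the safer main presentation: the criteria differ for ventilated patients, and background risk may differ between ICU and floor. The argument for pooling is strong only for attributed SAEs.

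**Conclusion.** The point holds as a mismatch between stated endpoints and stated analysis. Followed as written, Section 7.1 would summarise proportions that differ from both primary safety endpoints, and no estimate of attributed SAEs would use the whole trial. For attributed SAEs with no events, pooling lowers the 95% upper bound to 2.8%, from 8.6% and 4.0% by cohort.

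These bounds assume that all 131 planned patients are infused and that two-sided 95% limits apply. An early halt under Section 12.2 would make the denominators smaller. The pooled figure is an average weighted 41/131 = 31% ICU and 90/131 = 69% non-ICU, a mix set by efficacy power, so it belongs beside the cohort results and does not replace them. None of the bounds concerns 12-hour deterioration. The change should be made, but the efficacy design is unaffected.

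**What to change.** Add to Section 7.1, among subjects who received plasma:

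- **Attributed SAEs:** the number and proportion with at least one plasma-attributed SAE, with exact Clopper-Pearson 95% intervals, pooled over all infused subjects (planned n = 131) and by cohort.
- **12-hour deterioration:** the number and proportion meeting the Section 4.1 definition, with exact 95% intervals, by cohort as the main presentation. Any pooled figure is supportive only.
- **Window and deaths:** one follow-up window for attributed SAEs, after the 30-day and 60-day periods in Sections 11.2.1, 11.2.3 and 11.3 are reconciled. State that a subject who dies without an attributed SAE stays in the denominator as a non-event, and report how many were lost before the window closed.
- **Supporting tables:** keep the overall SAE and Grade 3+ proportions.

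The cost is a few sentences and one extra table. Causality is already recorded. For the 12-hour endpoint the team should confirm that FiO2, PEEP and support type can be taken from routine records, because Table 1 schedules post-infusion vital signs only to 30–60 minutes and daily assessments after that.
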